**Table UP 1 UPDRS total scores for all Parts (Full analysis set)**

Use the same format as for Table UD 1. Include all visits with UPDRS data in the table. Produce the table above for PPS as well, providing there is any de facto difference between the analysis sets. If the LMM is performed using transformed data, insert a footnote about this as well. If the LMM approach is dropped in favour of non-parametric tests, update the table and footnotes accordingly.

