## 8 STUDY DESIGN

### 8.1 Overall study design and schedule of events

This is a two-arm, double-blind, randomized, placebo-controlled Phase 2a study evaluating the safety, tolerability, and preliminary efficacy of up to 2 mg/day of NLX-112 versus placebo in patients with moderate to severe L-DOPA induced dyskinesia (LID) in Parkinson's disease (PD). NLX-112 will be up-titrated to either 2 mg/day (1 mg BID) or to the highest well-tolerated dose less than 2 mg/day over 4 weeks, maintained at the well-tolerated dose for an additional 2 weeks, and then down-titrated over 2 weeks. An overview of the study design is shown in Figure 1.

Patients will report to the study clinic for a screening visit (Visit 1), followed by a baseline visit on Day 1 (Visit 2) where patients will be randomized and begin treatment. Two remote safety visits over telephone (Days 7 and 49 [Visit 3 and Visit 8]) will be conducted. Once treatment has commenced, there will be 2 in-person safety visits to the clinic (Days 14 and 21 [Visit 4 and Visit 5]), 2 in-person efficacy visits to the clinic (Days 28 and 42 [Visit 6 and Visit 7]) and one follow-up in-person final safety visit (Day 70 [Visit 9]). In total, patients will report to the clinic for 7 in-person visits. Patients entering the study will be randomized in a 2:1 ratio (16:8 patients) to receive either NLX-112 or placebo.

[figure not shown]
At Visits 2, 6 and 7, efficacy assessments will start 30 minutes after the patient has taken 150% of his or her regular L-DOPA dose, when the patient is ON and experiencing typical dyskinesia.

The order of assessments at each visit is specified in Section 8.2.

A PD Home Dyskinesia Diary (electronic) will be completed by the patients and/or caregiver with concordance in ON time with dyskinesia between study staff and patient. Two consecutive 24-hour diaries will be completed prior to randomization (baseline, Visit 2) and prior to the clinic visits on Days 28 and 42 (Visits 6 and 7).

A wearable dyskinesia assessment device will be used to monitor dyskinesias during a 2-day period prior to the baseline visit (Day 1, Visit 2) and a 2-day period prior to the clinic visits on Days 28 and 42 (Visits 6 and 7, respectively).

Blood will be collected for possible NLX-112 plasma concentration measurements on Days 14, 21, 28, 42 and 70 (Visits 4, 5, 6, 7 and 9).

**Figure 1** Overview of study design

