Study day	Protocol Section	Day -28 to Day -5	Day 1	Day 7 ±1 day	Day 14 ±2 days	Day 21 ±2 days	Day 28 ±2 days	Day 42 ±2 days	Day 49 ±2 days	Day 70 ±7 days
Diary data collection 	11.3.3		X				X	X		
Wearable device data collection 	11.3.6		X				X	X		
L-DOPA challenge	11.3.1		X				X	X		
UDysRS	11.3.2		X				X	X		
Video taping (UDysRS)	11.3.2		X				X	X		
CGI-S/CGI-C 	11.3.5		X				X	X		
KPPS	11.4.1		X				X	X		
PDQ39	11.4.2		X				X	X		
HADS	11.4.3		X				X	X		
ICIQ-OAB	11.4.4		X				X	X		
ESS	11.4.5		X				X	X		
NLX-112 plasma concentration sampling	11.4.6				X	X	X	X		X
Drug accountability	10.5						X	X		X
Baseline symptoms	11.1.10	X								
Adverse events 	11.2.1						X			
Prior and concomitant medications	11.1.6						X			

CGI-S/CGI-C=Clinical Global Impression of Severity and Clinical Global Impression of Change, C-SSRS=Columbia Suicide Severity Rating Scale, ESS=the Epworth Sleepiness Scale, HADS=the Hospital Anxiety Depression Scale, ICIQ-OAB=the International Consultation on Incontinence Questionnaire Overactive Bladder Module,

KPPS=the King's Parkinson's disease Pain Scale, UPDRS=the Unified Parkinson's Disease Rating Scale, MMSE=Mini Mental Status Exam, PDQ39=the Parkinson's disease Quality of Life Scale (39-item), UDysRS=the Unified Dyskinesia Rating Scale

1. Also early withdrawal follow-up visit
2. Confirmation of eligibility
3. Blood pressure (including orthostatic hypotension assessment), pulse, respiratory rate and temperature. At screening and baseline (Visit 1 and Visit 2), vital signs to assess orthostatic hypotension will be conducted in triplicate, 15-20 minutes apart, with the average of the 3 assessments used for exclusion.
4. Body weight at Visit 1 and Visit 9. Height at Visit 1 only.
5. The Modified Hoehn and Yahr scale will be used to establish the PD stage of the patient.
6. Women of child-bearing potential only.
7. Hematology, coagulation, serum biochemistry and urinalysis.
8. C-SSRS: the baseline scale will be used at the first assessment (screening, Visit 1) and the follow-up scale will be used at all subsequent visits.
9. UPDRS - Screening: part IV only. Other visits: parts I-IV
10. PD Home Dyskinesia Diary: 2 consecutive 24-hour diaries taken prior to the visits indicated above.
11. Wearable data collection will take place during a 2-day period prior to the visits indicated above.
12. CGI-S at baseline (Day 1, Visit 2), CGI-C at other visits.

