**Table 8.2-1 Order of efficacy assessments**

Assessment	Assessor	
	Investigator	Patient
UDysRS (Parts III and IV repeated 3 times at approximately 30, 60 and 90 minutes after the 150% L-DOPA challenge)	X	
UPDRS part III in ON (within 30-90 minutes after the 150% L-dopa challenge)	X	
UPDRS parts I, II and IV	X	X 
CGI-C	X	
KPPS	X	
UDysRS (Parts I and II)		X
PDQ39		X
HADS		X
ESS		X
ICIQ-OAB		X

CGI-C=Clinical Global Impression of Change, ESS=the Epworth Sleepiness Scale, HADS=the Hospital Anxiety Depression Scale, ICIQ-OAB=the International Consultation on Incontinence Questionnaire Overactive Bladder Module, KPPS=the King's Parkinson's disease Pain Scale, UPDRS=Unified Parkinson's Disease Rating Scale, PDQ39=the Parkinson's disease Quality of Life Scale (39-item), UDysRS=the Unified Dyskinesia Rating Scale

End of Part I and Part II

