### 9.2 Analysis of secondary endpoints

#### 9.2.1 *Statistical inferential analysis of efficacy endpoints*

Absolute change from baseline in efficacy endpoints (secondary and exploratory endpoints) will generally be analysed using a linear mixed model with treatment, visit and the interaction

treatment\*visit as fixed categorical effects and subject within treatment as a random effect. The baseline value of the dependent variable will be included in the model as a continuous covariate, to account for possible differences in change from baseline outcomes due the starting baseline level. Visit will be modelled as a repeated effect. Kenward-Roger's approximation for degrees of freedom will be used.

Providing a significant type III F-test for the interaction effect treatment\*visit, differences between least square estimates of NLX-112 and placebo for the same visit (i.e. from the interaction term treatment\*visit, where visit is the same for both NLX-112 and placebo) will be estimated and the corresponding p-value will be presented in tables. In addition, differences between least square estimates of each post-baseline visit and baseline for NLX -112 and placebo respectively (i.e. from the interaction term treatment\*visit, where treatment is the same for the post-baseline and the baseline visit) will be estimated and the corresponding p-value will be presented in tables.

The model proposed above will be used for FAS and is valid, as long as the underlying data is missing at random (MAR). As a sensitivity analysis, the model will also be run for PPS, serving as a validity check for the main FAS analysis. The sensitivity analysis will be a complete case analysis, i.e., only patients with no missing data for the dependent variable will be used.

Model diagnostics, for example Shapiro-Wilk's test for a normally distributed residual term and Leven's test for the homoscedasticity assumption of the residual term as well as Q-Q plots and plotting residuals vs. predicted values, will be performed. If model assumptions are deemed to be violated, an attempt will be made to transform the dependent variable in order to fulfil model diagnostics.

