#### **9.2.4 Unified Parkinson's Disease Rating Scale (UPDRS)**

Change from baseline in UPDRS combined scores (Parts I, II, III and IV) to Visit 6 (Day 28) and Visit 7 (Day 42) respectively will be summarized using descriptive statistics. UPDRS combined scores will be analysed using inferential statistics as described under 9.2.1 above. The same analysis will be done for UPDRS Part III only.

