### 10.2.3 Secondary endpoint(s)

#### 10.2.3.1 Unified Dyskinesia Rating Scale (UDysRS) total score

**Table UD 1 UDysRS total score for all Parts (Full analysis set)**

Result category	Assessment timepoint		NLX-112 (N=XX)	Placebo (N=XX)	Total (N=XX)
Measured value	[Assessment timepoint 1]	n	xx	xx	xx
		Mean (SD)	x.xx (x.xx)	x.xx (x.xx)	x.xx (x.xx)
		Median (Min, Max)	x.xx (x.x, x.x)	x.xx (x.x, x.x)	x.xx (x.x, x.x)
	[Assessment timepoint 2]	n	xx	xx	xx
		...	...	...	...
Absolute change from baseline	[Assessment timepoint 2]	n	xx	xx	xx
		Mean (SD)	x.xx (x.xx)	x.xx (x.xx)	x.xx (x.xx)
		Median (Min, Max)	x.xx (x.x, x.x)	x.xx (x.x, x.x)	x.xx (x.x, x.x)
	[Assessment timepoint 3]	LMM a p-value	xxxxx b	xxxxx c	xxxxx d
		n	xxxxx	xxxxx	xxxxx
		...	...	...	...
Relative change from baseline (%)	[Assessment timepoint 2]	n	xx	xx	xx
		Mean (SD)	x.xx (x.xx)	x.xx (x.xx)	x.xx (x.xx)
		Median (Min, Max)	x.xx (x.x, x.x)	x.xx (x.x, x.x)	x.xx (x.x, x.x)
	[Assessment timepoint 3]	n	xxxxx	xxxxx	xxxxx
		...	...	...	...

a) Linear mixed model (LMM) with treatment, visit and the interaction treatment\*visit as fixed categorical effects and subject within treatment as a random effect. The baseline value of the dependent variable has been included in the model as a continuous covariate. Kenward-Roger's approximation for degrees of freedom will be used.

b) p-value for the difference between NLX-112 at the assessment timepoint and at baseline.

c) p-value for the difference between placebo at the assessment timepoint and at baseline.

d) p-value for the difference between NLX-112 and placebo absolute change from baseline at the assessment timepoint.

Data based on the Full analysis set. The session marked as most severe for Part III and IV have been used. For Part III, the highest score for each individual questionnaire item has been used. All UDysRS item scores for Part I, II, III and IV have been summarized pre patient and assessment timepoint and used as input data to the table. N: Number of observations. SD: Standard deviation. NC: Not calculated - number of evaluable observations less than 3. NA: Not available - no evaluable observations. SAS program: [PROGRAM NAME].sas. Run by: [USERNAME] YYYY-MM-DDTHH:MM:SS. Data extracted at: YYYY-MM-DDTHH:MM:SS

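### The UPDRS table shells ask for every UPDRS visit in a format with model p-values, so read literally the off-drug, unchallenged Visit 9 enters an analysis that SAP 9.2.4 confines to Visits 6 and 7

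*SAP*

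**What the plan says.** SAP 9.2.4 defines the UPDRS summary as "Change from baseline in UPDRS combined scores (Parts I, II, III and IV) to Visit 6 (Day 28) and Visit 7 (Day 42) respectively", sends the inference to 9.2.1, and repeats the analysis for Part III alone. Protocol 17.6.3 names the same two visits.

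The shells in SAP 10.2.3.3 go further. Table UP 1 takes the format of Table UD 1 and adds "Include all visits with UPDRS data in the table"; Table UP 2 (Part III) carries the same instruction. Under absolute change, the UD 1 format has an LMM p-value row with two within-arm p-values and a between-arm one, footnoted as "p-value for the difference between NLX-112 and placebo absolute change from baseline at the assessment timepoint".

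SAP 9.2.1 fits treatment, visit and their interaction. Visit-specific treatment contrasts are conditional: "Providing a significant type III F-test for the interaction effect treatment" by visit. The within-arm contrasts are to be made at each post-baseline visit, and no sentence says which visits enter. The sensitivity run on the PPS is a complete-case analysis on the dependent variable.

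In the protocol's Table 8.1-1, UPDRS is scheduled at Visits 1, 2, 6, 7 and 9. The footnote reads "UPDRS - Screening: part IV only. Other visits: parts I-IV". Protocol 8.1 describes Visit 9 as "one follow-up in-person final safety visit (Day 70 [Visit 9"; the schedule gives it a ±7-day window and also uses it as the early-withdrawal visit. The L-DOPA challenge is scheduled only at Visits 2, 6 and 7. At those visits Table 8.2-1 calls for "UPDRS part III in ON (within 30-90 minutes after the 150% L-dopa challenge"). No motor state is given for Visit 9.

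**The concern.** A programmer working from the shells has an instruction to include Visit 9, a format that assigns it p-values, and a model section that does not exclude it. Three things then follow.

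- **Within-arm p-values.** SAP 5.1 says these tests aim to show a beneficial shift from baseline caused by the IMP. At Visit 9 patients are off drug and unchallenged, while baseline Part III was rated after the 150% challenge. A within-arm change in Part III, or in the combined score that contains it, mixes loss of challenge with loss of drug.
- **Complete-case PPS run.** If Visit 9 is part of the dependent variable, a patient with full Day 28 and Day 42 data but no Visit 9 rating drops out.
- **Interaction gate.** The gate decides whether Day 28 and Day 42 contrasts are shown. With Visit 9 in the model it largely tests on-drug against off-drug, not Visit 6 against Visit 7. UPDRS is the only efficacy scale scheduled at Visit 9, so this would affect UPDRS alone.

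**Working it through.** **Reference figure.** The plan gives no power, effect size or SD (SAP 5.2), so there is none to reproduce. Allocation is 2:1 in 24 patients, that is 16 and 8 (SAP 4.3). Tests are two-sided at 5% (SAP 5.7).

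**Time off drug at Visit 9.** The last planned dose is on Day 56 (protocol 8.1), and the window runs from Day 63 to Day 77, so patients are 7 to 21 days off drug. With a half-life of 34 to 41 h (protocol 6.1.3):

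- Day 63: 168 h, or 168/41 = 4.1 to 168/34 = 4.9 half-lives
- Day 70: 336 h, or 8.2 to 9.9 half-lives
- Day 77: 504 h, or 12.3 to 14.8 half-lives

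These intervals apply to patients who complete treatment. An early-withdrawal assessment recorded under Visit 9 can fall on another study day.

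**Probability that the gate opens.** I took complete data and compound symmetry. The baseline covariate is constant across visits and drops out of the interaction. With k visits, treatment effects d_v in SD units and within-patient correlation ρ:

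- F has (k−1) and (k−1)(24−2) degrees of freedom
- noncentrality λ = Σ(d_v − mean d)² × (16×8/24) / (1−ρ), where 16×8/24 = 5.333

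Visits 6 and 7 only, equal effect d: every deviation is zero, so λ = 0. The test is F(1,22) and the gate opens 5% of the time at any effect size.

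Visits 6, 7 and 9 with effects d, d, 0: the mean is 2d/3 and the squared deviations sum to d²(1/9 + 1/9 + 4/9) = 2d²/3. The test is F(2,44) with λ = (2/3)d² × 5.333/(1−ρ). For d = 1 and ρ = 0.5, λ = 7.11.

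| ρ | d = 0.5 | d = 0.8 | d = 1.0 |
|---|---|---|---|
| 0.5 | 19% | 44% | 63% |
| 0.7 | 30% | 66% | 86% |
| 0.8 | 43% | 84% | 96% |

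**Checks by simulation** (20,000 trials per setting, ρ = 0.7):

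- d = 0.8: 4.9% without Visit 9 and 66.2% with it.
- d = 0.8, with a 2 SD shift at Visit 9 common to both arms: 66.4%. A missing challenge that moves both arms equally does not drive the interaction.
- No drug effect, with the same common shift: 5.2%.
- d = 0.8, with the SD at Visit 9 1.5 times larger: 44%.

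A between-arm Hotelling test on the visit differences, which does not assume compound symmetry, gives 60% (ρ = 0.5) and 82% (ρ = 0.7) at 1 SD, close to the table.

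**If the effect persists at Visit 9**, the gate stays at 5% with all three visits.

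**After restriction to Visits 6 and 7.** If the Visit 6 effect is half the Visit 7 effect, the squared deviations sum to 0.125d², and the gate opens in 9% to 42% of trials over the same grid (21% at d = 0.8, ρ = 0.7). If the effect is equal at both visits, it opens in 5%.

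**Visit 1.** Only Part IV is rated, so neither the combined score (UP 1) nor Part III (UP 2) can be formed there.

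**The case against.** The instruction concerns what appears in the table. Methods belong in SAP section 9, where 9.2.4 names Visits 6 and 7. SAP Table 2 lists the departures from the protocol, including the longer diary and wearable window, and has no entry for adding Visit 9 to UPDRS inference. The UD 1 format also has rows without p-values, so extra visits could be shown descriptively. That the instruction literally covers Visit 1, where neither score exists, suggests loose wording. This stands: entry of Visit 9 into the model is an inference from the format and from 9.2.1, and the plan nowhere states it.

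A reader might infer that every Visit 9 p-value is uninterpretable. That goes too far. If the missing challenge shifts both arms equally, it falls into the visit main effect, and NLX-112 against placebo at Visit 9 remains a readable off-drug comparison. The difficulty lies mainly in the within-arm p-values, and the challenge timing in Table 8.2-1 is attached to Part III, not to Parts I, II and IV.

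A reader might also take the gate figures as false-positive inflation, or as a reason why removing Visit 9 suffices. Neither holds. With no drug effect the gate stays near 5%. With a true constant effect, removing Visit 9 makes the Day 28 and Day 42 results less likely to be shown, because the two-visit gate cannot see a constant effect.

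Finally, SAP 5.1 and 5.8 call the tests indicative and exploratory, and individual UPDRS data are listed anyway. This limits the severity.

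**Conclusion.** The shells and SAP 9.2.4 disagree about which visits carry UPDRS inference, and nothing in 9.2.1 settles it. On the literal reading, Visit 9 receives p-values contrary to SAP 9.2.4 and protocol 17.6.3. Its within-arm tests for Part III and the combined score do not measure a shift due to the IMP, and the complete-case PPS run could lose patients who lack only Visit 9.

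On the same reading the choice of visits largely determines whether Day 28 and Day 42 contrasts are reported: 19% to 96% with Visit 9 against 5% without. This range rests on assumed effects of 0.5 to 1.0 SD, equal at Visits 6 and 7 and fully washed out at Visit 9, a correlation of 0.5 to 0.8, equal variances and complete data. A larger variance at Visit 9 lowers the figures, and an effect that persists to Visit 9 removes the difference.

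Severity is minor to moderate. UPDRS is a secondary endpoint and the comparison is exploratory.

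**What to change.** State in SAP 9.2.4 and in Tables UP 1 and UP 2 that the mixed model, its p-values and the complete-case rule use Visits 6 and 7 only. Show Visit 9 as descriptive rows without p-values, labelled as off treatment and without L-DOPA challenge, and identify early-withdrawal assessments as such. Note that Visit 1 contributes to neither table.

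Make one further change with it: report the UPDRS Day 28 and Day 42 treatment contrasts regardless of the interaction test. Otherwise the two-visit gate would hide a constant effect in about 95% of trials.

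The cost is SAP and shell wording, with a small programming change. No data collection changes.

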**Table UP 2 UPDRS total scores for Part III (Full analysis set)**

Use the same format as for Table UD 1. Include all visits with UPDRS data in the table. Produce the table above for PPS as well, providing there is any de facto difference between the analysis sets. If the LMM is performed using transformed data, insert a footnote about this as well. If the LMM approach is dropped in favour of non-parametric tests, update the table and footnotes accordingly.

*10.2.3.4 Clinical Global Impression of Change (CGI-C) in overall PD symptoms*
**Table CG 1 CGI-S and CGI-C in overall PD symptoms (Full analysis set)**

Assessment	Assessment timepoint		NLX-112 (N=XX)	Placebo (N=XX)	Total (N=XX)
CGI-S	[Assessment timepoint 1]	n	xx	xx	xx
		Mean (SD)	x.xx (x.xx)	x.xx (x.xx)	x.xx (x.xx)
		Median (Min, Max)	x.xx (x.x, x.x)	x.xx (x.x, x.x)	x.xx (x.x, x.x)
CGI-C	[Assessment timepoint 2]	n	xx	xx	xx
		Mean (SD)	x.xx (x.xx)	x.xx (x.xx)	x.xx (x.xx)
		Median (Min, Max)	x.xx (x.x, x.x)	x.xx (x.x, x.x)	x.xx (x.x, x.x)
CGI-C	[Assessment timepoint 3]	LMM a p-value	xxxxx b	xxxxx c	xxxxx d
		n	xx	xx	xx
		Mean (SD)	x.xx (x.xx)	x.xx (x.xx)	x.xx (x.xx)
		Median (Min, Max)	x.xx (x.x, x.x)	x.xx (x.x, x.x)	x.xx (x.x, x.x)
		LMM a p-value	xxxxx b	xxxxx c	xxxxx d

Data based on the Full analysis set. SAS program: [PROGRAM NAME].sas. Run by: [USERNAME] YYYY-MM-DDTHH:MM:SS. Data extracted at: YYYY-MM-DDTHH:MM:SS

Specify CGI-S or CGI-C in the assessment column. Do not include rating 0, indicating “no assessment” in the summary/analysis. There is no result category column, since change from baseline is included in the definition of CGI-C. Produce the table above for PPS as well, providing there is any de facto difference between the analysis sets. If the LMM is performed using transformed data, insert a footnote about this as well. If the LMM approach is dropped in favour of non-parametric tests, update the table and footnotes accordingly.

*10.2.3.5 Dyskinesia scores measured by a wearable dyskinesia assessment device*
**Table DA 1 Kinesia 360 wearable dyskinesia assessment system (Full analysis set)**

Use the same format as for Table UD 1. Add a footnote describing that the mean values per patient and visit have been used as input data to the table. Produce the table above for PPS as well, providing there is any de facto difference between the analysis sets. If the LMM is performed using transformed data, insert a footnote about this as well. If the LMM approach is dropped in favour of non-parametric tests, update the table and footnotes accordingly.

## 10.2.4 Exploratory endpoint(s)

### 10.2.4.1 King's Parkinson's Disease Pain Scale (KPPS) total score

**Table KP 1 KPPS individual pain domains scores and total score (Full analysis set)**

Assessment (unit)	Result category	Assessment timepoint		NLX-112 (N=XX)	Placebo (N=XX)	Total (N=XX)
[PARAMETER 1] (unit)	Measured value	[Assessment timepoint 1]	n	xx	xx	xx
			Mean (SD)	x.xx (x.xx)	x.xx (x.xx)	x.xx (x.xx)
			Median (Min, Max)	x.xx (x.x, x.x)	x.xx (x.x, x.x)	x.xx (x.x, x.x)
	Absolute change from baseline	[Assessment timepoint 2]	n	xx	xx	xx
			...	...	...	...
			n	xx	xx	xx
	Relative change from baseline (%)	[Assessment timepoint 2]	Mean (SD)	x.xx (x.xx)	x.xx (x.xx)	x.xx (x.xx)
			Median (Min, Max)	x.xx (x.x, x.x)	x.xx (x.x, x.x)	x.xx (x.x, x.x)
			LMM a p-value	xxxxx b	xxxxx c	xxxxx d

Data based on the Full analysis set. n: Number of observations. SD: Standard deviation. NC: Not calculated - number of evaluable observations less than 3. NA: Not available - no evaluable observations. SAS program: [PROGRAM NAME].sas. Run by: [USERNAME] YYYY-MM-DDTHH:MM:SS. Data extracted at: YYYY-MM-DDTHH:MM:SS

Produce the table above for PPS as well, providing there is any de facto difference between the analysis sets. If the LMM is performed using transformed data, insert a footnote about this as well. If the LMM approach is dropped in favour of non-parametric tests, update the table and footnotes accordingly.

### 10.2.4.2 Parkinson's Disease Questionnaire (PDQ39) total score

**Table PD 1 PDQ39 calculated dimensions scores and total score (Full analysis set)**

Use the same format as for Table KP 1. Produce the table above for PPS as well, providing there is any de facto difference between the analysis sets. If the LMM is performed using transformed data, insert a footnote about this as well. If the LMM approach is dropped in favour of non-parametric tests, update the table and footnotes accordingly.

